## 10.9. Interim Analyses

Since this is a Phase 1 study, safety data will be reviewed on an ongoing basis.

For Dosages C and D (patients with breast cancer), interim analyses will be conducted in each dosage to review available safety, efficacy, PK, and pharmacodynamic data after 5 patients in that particular dosage have either completed approximately 3 cycles of therapy or discontinued from the treatment. If 2 or more responders are observed, an additional 5 patients will be enrolled. Further interim analysis may be considered if deemed appropriate by the sponsor.

If it is deemed that enough data are obtained to assess the primary objective and the secondary objectives, a clinical study report might be created before the last patient visit. In this case, all data until the data cutoff date will be used for the analysis of safety, efficacy, PK, and pharmacodynamic biomarkers. All data defined in the protocol will continue to be collected from patients on treatment after the data cutoff date. These data may be reported separately, and the analyses on all patients including these data may not be performed.

## 11. Informed Consent, Ethical Review, and Regulatory Considerations

### 11.1. Informed Consent

The investigator is responsible for ensuring that the patient understands the potential risks and benefits of participating in the study, including answering any questions the patient may have in regard to the study procedures and patient requirements throughout the study and sharing in a timely manner any new information that may be relevant to the patient's willingness to continue his or her participation in the study in a timely manner.

The ICF will be used to explain the potential risks and benefits of study participation to the patient in simple terms before the patient is entered into the study and to document that the patient is satisfied with his or her understanding of the potential risks and benefits of participating in the study and desires to participate in the study.

The investigator is ultimately responsible for ensuring that informed consent is given by each patient or legal representative before the study is started. This includes obtaining the appropriate signatures and dates on the ICF prior to the performance of any protocol screening procedures and prior to the administration of study drug.

In this protocol, the term "informed consent" includes all consent and assent given by patients or their legal representatives.

### 11.2. Ethical Review

Lilly or its representatives must approve all ICFs before they are used at investigative sites(s). All ICFs must be compliant with the ICH guideline on GCP.

Documentation of ERB approval of the protocol and the ICF must be provided to Lilly before the study may begin at the investigative site(s). The ERB(s) will review the protocol as required.

The study site's ERB(s) should be provided with the following prior to any study activities and during the course of the trial for any amendments/addendums or administrative notifications:

- the current IB
- ICF
- relevant curricula vitae

### 11.3. Regulatory Considerations

This study will be conducted in accordance with:

- 1) consensus ethics principles derived from international ethics guidelines, including the Declaration of Helsinki and Council for International Organizations of Medical Sciences International Ethical Guidelines
- 2) ICH GCP Guideline [E6]
- 3) applicable laws and regulations

The investigator or designee will promptly submit the protocol to applicable ERB(s).

Some of the obligations of the sponsor will be assigned to a TPO.

An identification code assigned by the sponsor to each patient will be used in lieu of the patient's name to protect the patient's identity when reporting AEs and/or other study-related data.

#### 11.3.1. Investigator Information

Site-specific contact information may be provided in a separate document.

#### 11.3.2. Protocol Signatures

The sponsor's responsible medical officer will approve the protocol, confirming that, to the best of his or her knowledge, the protocol accurately describes the planned design and conduct of the study.

After reading the protocol, each principal investigator will sign the protocol signature page and send a copy of the signed page to a Lilly representative along with the IB acknowledgement form.

#### 11.3.3. Final Report Signature

The investigator or designee will sign the clinical study report for this study, indicating agreement with the analyses, results, and conclusions of the report.

The sponsor's responsible medical officer and statistician will approve the final clinical study report for this study, confirming that, to the best of his or her knowledge, the report accurately describes the conduct and results of the study.

**Attachment 1.     Protocol JSCB Study Schedules**

---

## Baseline and Cycle 1 Assessments (for All Dosing Schedules)

Procedure	Baseline Relative Day Prior to Day 1 of Cycle 1			Treatment Cycle 1 only					Comments	
	≤28	≤14	≤7	Day 1	Day 8	Day 15	Day 22	Day 29	Day 36	
	Except for the Cycle 1, Day 1 visit, allowable visit windows are ±3 days, unless indicated otherwise.									
Eligibility Assessments										
Informed consent	X									
Medical history		X								
β-hCG Pregnancy test			X							At baseline, a urine or serum pregnancy test is required for WOCBP. Thereafter, every 12 weeks after the first dose or according to local regulations, whichever is more frequent.
ECG		X			X			X		Note that in cases where ECG and blood sample collection are scheduled at the same time, all blood sampling should be performed prior to ECG assessment.
ECOG PS assessment		X		X	X	X	X	X		
Safety Assessments										
Physical examination		X		X		X		X		Includes height (at baseline only), and thoracic, abdominal, and symptom-directed examination.
Vital signs and weight measurement		X		X	X	X	X	X		Vital signs include temperature, pulse rate, respiration rate, and blood pressure. Vital signs will be checked and recorded prior to each infusion of LY3022855, midway through each infusion, at the end of each infusion, and every 15 minutes for the first hour following each infusion, including Cycle 1, Day 1 (also to be checked and recorded at nontreatment visits during Cycle 1).
Toxicity/AE assessment		X		X	X	X	X	X		Any preexisting toxicity should be documented, recorded, and graded (CTCAE v4.0 grade) as a part of the baseline medical history.  AEs that are serious, considered related to study treatment or the study, or that caused the patient to discontinue before completing the study should be followed until the event is resolved, the event is no longer considered to be drug-related, the event becomes stable or returns to baseline, a new treatment is initiated for the patient, or the patient dies or is lost to follow-up. Frequency of AE and SAE follow-up evaluation is left to the discretion of the investigator. Data on SAEs that occur before the end of the trial will be stored in the collection database and the Lilly Safety System.
Concomitant medication assessment		X		X	X	X	X	X		Including those medications taken within 28 days prior to the first dose of study therapy.

Procedure	Baseline Relative Day Prior to Day 1 of Cycle 1			Treatment Cycle 1 only						Comments
	≤28	≤14	≤7	Day 1	Day 8	Day 15	Day 22	Day 29	Day 36	
Laboratory Tests										
HIV and viral hepatitis B and C screening	X*									Includes HIV and hepatitis B and C, per institutional standards. If done within 28 days prior to Cycle 1, Day 1 as part of standard of care, does not need to be repeated. * Should be done within 60 days prior to enrollment.
Hematology		X		X	X	X	X	X	X	Every week for the first 12 weeks on therapy.
Coagulation		X					X*			Evaluations performed as part of the baseline assessment do not need to be repeated on Cycle 1, Day 1, unless required in the opinion of the investigator. * Required within 14 days of planned posttreatment tumor biopsy.
Serum chemistry		X		X	X	X	X	X	X	Every week for the first 12 weeks on therapy.
CEA and CA 15-3	X									Applies only to breast cancer cohorts and if clinically applicable.
C-reactive protein assessment		X		X	X	X	X	X	X	Every week for the first 12 weeks on therapy, and every 2 weeks thereafter.
Urinalysis		X								Evaluations performed as part of the baseline assessment do not need to be repeated on Cycle 1, Day 1, unless required in the opinion of the investigator. Urinalysis evaluations will be performed at the beginning of each cycle (that is, approximately every 6 weeks following the first dose of study therapy). If urine dipstick >1+ for protein, obtain 24-hour urine collection for protein analysis.
Serum and urine myoglobin		X*		X*	X*	X*	X*	X*	X*	*As clinically indicated, if serum CK $\geq 2.5 \times$ ULN.
Tailoring biomarkers	X									10 mL of blood to be drawn for future pharmacogenetic biomarker testing.
Blood sampling for PK, PD, IG	Refer to Attachment 4 , Attachment 5 , and Attachment 6 .						All sampling indicated in Attachment 4 , Attachment 5 , and Attachment 6 is to be done only after study eligibility is met.			
Efficacy Assessments										
Imaging studies (CT/MRI)	X*								X	Radiographic assessment of tumor response should be performed prior to the start of a cycle so that results are available before the patient receives a new cycle of treatment. If done within 28 days prior to Cycle 1, Day 1, as part of standard of care, does not need to be repeated prior to the start of Cycle 1. * For patients with treated CNS metastases that are eligible for this study, a baseline MRI documenting disease stability within 60 days prior to enrollment is required.

Procedure	Baseline Relative Day Prior to Day 1 of Cycle 1			Treatment Cycle 1 only						Comments
	≤28	≤14	≤7	Day 1	Day 8	Day 15	Day 22	Day 29	Day 36	
Bone scan	X								X*	
Breast cancer cohort: A baseline bone scan is required, except in the event that a PET scan is performed within 28 days prior to the first dose of study therapy that is negative for bone disease. Routine bone scans during treatment are not required, except in the setting of bone-only disease (no lymph node, visceral, skin, or subcutaneous metastases), or as deemed appropriate by the investigator.
 
*Prostate cancer cohort: Bone scans are required at baseline and (follow-up [posttreatment]) every 6 weeks thereafter, or as clinically indicated.
 
If done within 28 days prior to Cycle 1, Day 1, as part of standard of care, does not need to be repeated prior to the start of Cycle 1.

Tumor assessments	X								X	
Radiographic assessment of tumor response should be performed prior to the start of a cycle so that results are available before the patient receives a new cycle of treatment.
 
If done within 28 days prior to Cycle 1, Day 1, as part of standard of care, does not need to be repeated prior to the start of Cycle 1.

Tumor core needle or surgical biopsy		X							X	
Required: The first tumor biopsy will be taken (attempted) at baseline (predose), within 14 days prior to dosing on Cycle 1, Day 1, and the second tumor biopsy will be taken (attempted) within 14 days prior to dosing on Cycle 2, Day 1.
 
Optional: In cases of disease progression, if the patient's condition allows it, an optional tumor biopsy will be performed, as clinically indicated (refer to Section 8.2.2.2).

Ad hoc tumor tissue and blood sampling				X						
Optional: Additional tumor tissue and/or blood samples for biomarker research may be obtained at the investigator's discretion in discussion with the patient, such as at the time of radiographic response or treatment progression. If, at any time during the study, tumor tissue is obtained through a core biopsy, surgical biopsy, or resection as routine clinical care, the sponsor requests a tissue block or unstained slides for analysis of potentially relevant surrogate biomarkers.

Study Therapy Administration										
Administer LY3022855 Weekly (on Days 1, 8, 15, 22, 29, and 36)				X	X	X	X	X	X	
Administer LY3022855 Every 2 Weeks (on Days 1, 15, and 29)				X		X		X		
Administer LY3022855 on Weeks 1, 2, 4, and 5 (on Days 1, 8, 22, and 29)				X	X		X	X		

Abbreviations:  $\beta$ -hCG = beta human chorionic gonadotropin; AE = adverse event; CA 15-3 = cancer antigen 15-3; CEA = carcinoembryonic antigen; CK = creatine kinase; CNS = central nervous system; CT = computed tomography; CTCAE v4.0 = Common Terminology Criteria for Adverse Events, version 4.0; ECG = electrocardiogram; ECOG PS = Eastern Cooperative Oncology Group performance status; HIV = human immunodeficiency virus; ICF = informed consent form; IG = immunogenicity; MRI = magnetic resonance imaging; PET = positron emission tomography; PD = pharmacodynamic(s); PK = pharmacokinetic(s); SAE = serious adverse event; ULN = upper limit of normal; WOCBP = women of childbearing potential.

## Cycle 2 Assessments (for All Dosing Schedules)

Procedure	Treatment Cycle 2 only						Comments
	Day 1	Day 8	Day 15	Day 22	Day 29	Day 36	
Safety Assessments							
β-hCG Pregnancy test							Urine or serum pregnancy test is required for WOCBP every 12 weeks after the first dose or according to local regulations, whichever is more frequent.
ECG							Note that in cases where ECG and blood sample collection are scheduled at the same time, all blood sampling should be performed prior to ECG assessment.
ECOG PS assessment	X						To be performed only on dosing days. Dosing schedules, per protocol: Weekly (on Days 1, 8, 15, 22, 29, and 36), Every 2 Weeks (on Days 1, 15, and 29), or Weeks 1, 2, 4, and 5 (on Days 1, 8, 22, and 29).
Physical examination	X						Includes thoracic, abdominal, and symptom-directed examination.
Vital signs and weight measurement	X						To be performed only on dosing days. Dosing schedules, per protocol: Weekly (on Days 1, 8, 15, 22, 29, and 36), Every 2 Weeks (on Days 1, 15, and 29), or Weeks 1, 2, 4, and 5 (on Days 1, 8, 22, and 29).  Vital signs include temperature, pulse rate, respiration rate, and blood pressure. Vital signs will be checked and recorded prior to each infusion of LY3022855, midway through each infusion, at the end of each infusion, and every 15 minutes for the first hour following each infusion.
Toxicity/AE assessment	X						To be performed only on dosing days. Dosing schedules, per protocol: Weekly (on Days 1, 8, 15, 22, 29, and 36), Every 2 Weeks (on Days 1, 15, and 29), or Weeks 1, 2, 4, and 5 (on Days 1, 8, 22, and 29).  AEs that are serious, considered related to study treatment or the study, or that caused the patient to discontinue before completing the study should be followed until the event is resolved, the event is no longer considered to be drug-related, the event becomes stable or returns to baseline, a new treatment is initiated for the patient, or the patient dies or is lost to follow-up. Frequency of AE and SAE follow-up evaluation is left to the discretion of the investigator. Data on SAEs that occur before the end of the trial will be stored in the collection database and the Lilly Safety System.
Concomitant medication assessment	X						To be performed only on dosing days. Dosing schedules, per protocol: Weekly (on Days 1, 8, 15, 22, 29, and 36), Every 2 Weeks (on Days 1, 15, and 29), or Weeks 1, 2, 4, and 5 (on Days 1, 8, 22, and 29).
Laboratory Tests							
Hematology	X	X	X	X	X	X	Every week for the first 12 weeks on therapy.
Serum chemistry	X	X	X	X	X	X	Every week for the first 12 weeks on therapy.
CEA and CA 15-3	X						Applies only to breast cancer cohorts and if clinically applicable.
C-reactive protein assessment	X	X	X	X	X	X	Every week for the first 12 weeks on therapy, and every 2 weeks thereafter.

Procedure	Treatment Cycle 2 only						Comments
	Day 1	Day 8	Day 15	Day 22	Day 29	Day 36	
Urinalysis	X						Except for the Cycle 1, Day 1 visit, allowable visit windows are <math>\pm 3</math> days, unless indicated otherwise.
Serum and urine myoglobin	X*	X*	X*	X*	X*	X*	*As clinically indicated, if serum CK $\geq 2.5 \times$ ULN.
Blood sampling for PK, PD, IG	Refer to Attachment 4 , Attachment 5 , and Attachment 6 .						
Efficacy Assessments							
Imaging studies (CT/MRI)						X	Radiographic assessment of tumor response should be performed prior to the start of a cycle so that results are available before the patient receives a new cycle of treatment.
Bone scan						X*	Breast cancer cohort: Routine bone scans during treatment are not required, except in the setting of bone-only disease (no lymph node, visceral, skin, or subcutaneous metastases), or as deemed appropriate by the investigator. *Prostate cancer cohort: Follow-up (posttreatment) bone scans are required every 6 weeks, or as clinically indicated.
Tumor assessments						X	Radiographic assessment of tumor response should be performed prior to the start of a cycle so that results are available before the patient receives a new cycle of treatment.
Ad hoc tumor tissue and blood sampling	X						Optional: Additional tumor tissue and/or blood samples for biomarker research may be obtained at the investigator's discretion in discussion with the patient, such as at the time of radiographic response or treatment progression. If, at any time during the study, tumor tissue is obtained through a core biopsy, surgical biopsy, or resection as routine clinical care, the sponsor requests a tissue block or unstained slides for analysis of potentially relevant surrogate biomarkers.
Study Therapy Administration							
Administer LY3022855 Weekly (on Days 1, 8, 15, 22, 29, and 36),	X	X	X	X	X	X	
Administer LY3022855 Every 2 Weeks (on Days 1, 15, and 29)	X		X		X		
Administer LY3022855 Weeks 1, 2, 4, and 5 (on Days 1, 8, 22, and 29)	X	X		X	X		

Abbreviations:  $\beta$ -hCG = beta human chorionic gonadotropin; AE = adverse event; CA 15-3 = cancer antigen 15-3; CEA = carcinoembryonic antigen; CK = creatine kinase; CT = computed tomography; ECG = electrocardiogram; ECOG PS= Eastern Cooperative Oncology Group performance status; IG = immunogenicity; MRI = magnetic resonance imaging; PET = positron emission tomography; PD = pharmacodynamic(s); PK = pharmacokinetic(s); SAE = serious adverse event; ULN = upper limit of normal; WOCBP = women of childbearing potential.

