### Figure JSCB.3. Study JSCB study design.

Enrollment will be sequential, starting with the assignment of patients to Dosage A (LY3022855, 1.25 mg/kg every 2 weeks [Q2W] of a 6-week cycle), then the assignment of patients to Dosage B (LY3022855, 1.0 mg/kg on Weeks 1, 2, 4, and 5 of a 6-week cycle) once the Dosage A cohort is fully enrolled. Once the Dosage B breast cancer cohort is fully enrolled, patients with breast cancer will be assigned by the sponsor to Dosage C (LY3022855, 100 mg QW of a 6-week cycle) or D (LY3022855, 100 mg Q2W of a 6-week cycle) on an alternating basis until 5 patients are enrolled to each of Dosages C and D. Once 5 patients are enrolled to each of Dosages C and D, the sponsor and the investigators will review clinical data to determine if enrollment of an additional 5 patients to each of Dosages C and D is warranted (refer to Section 10 for details regarding sample size).

Patients will receive Dosage A, B, C, or D for one 6-week cycle or until the patient meets one or more criteria for study discontinuation. After 1 cycle, patients who are benefitting from study treatment (that is, no disease progression or unacceptable toxicity) may continue to receive study treatment at the same dose and schedule until there is clear (confirmed) evidence of disease progression or other withdrawal criteria are met. At the time of study completion, if a patient continues to benefit from study treatment, that patient may enter the continued access period.

Immune studies will include evaluations of changes in baseline over time in: (1) peripheral blood immune cell subsets, as determined by flow cytometric analysis using an antibody panel, and that may include but not be limited to the following markers: Live-Dead, CD3, CD4, CD8, CD14, CD16, FoxP3, PD-1, Ki-67, CTLA-4, TIM-3, LAG-3, and ICOS, as well as (2) serum cytokines, as determined by MSD multiplex cytokine immunoassay technology or ELISA, and that may include but not be limited to CSF-1, IFN- $\gamma$ , IL-1 $\beta$ , IL-2, IL-4, IL-6, IL-8, IL-10, IL-12p70, IL-13, IL-34, and TNF- $\alpha$ . Blood samples for the immunomodulatory studies will be taken as described in [Attachment 4](#), [Attachment 5](#), and [Attachment 6](#).

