Concomitant medication assessment	X						To be performed only on dosing days. Dosing schedules, per protocol: Weekly (on Days 1, 8, 15, 22, 29, and 36), Every 2 Weeks (on Days 1, 15, and 29), or Weeks 1, 2, 4, and 5 (on Days 1, 8, 22, and 29).

Procedure	Treatment Cycle 3 and beyond						Comments	
	Day 1	Day 8	Day 15	Day 22	Day 29	Day 36		
Laboratory Tests								
Hematology:								
For Weekly and Every-2-Week schedules	X		X		X		Cycle 3 and beyond: Every 2 weeks for patients receiving treatment on the Weekly or Every-2-Week dosing schedule (on Days 1, 15, and 29).	
For Weeks 1, 2, 4, and 5 schedule	X			X			Cycle 3 and beyond: Every 3 weeks for patients receiving treatment Weeks 1, 2, 4, and 5 (on Weeks 1 and 4 [that is, Days 1 and 22]).	
Serum chemistry:								
For Weekly and Every-2-Week schedules	X		X		X		Cycle 3 and beyond: Every 2 weeks for patients receiving treatment on the Weekly or Every-2-Week dosing schedule (on Days 1, 15, and 29).	
For Weeks 1, 2, 4, and 5 schedule	X			X			Cycle 3 and beyond: Every 3 weeks for patients receiving treatment Weeks 1, 2, 4, and 5 (that is, on Weeks 1 and 4 [that is, Days 1 and 22]).	
CEA and CA 15-3	X						Applies only to breast cancer cohorts and if clinically applicable.	
C-reactive protein assessment	X		X		X		Cycle 3 and beyond: Every 2 weeks.	
Urinalysis	X						Urinalysis evaluations will be performed at the beginning of each cycle (that is, approximately every 6 weeks following the first dose of study therapy). If urine dipstick $>1+$ for protein, obtain 24-hour urine collection for protein analysis.	
Serum and urine myoglobin	X*	X*	X*	X*	X*	X*	*As clinically indicated, if serum CK $\geq 2.5 \times$ ULN.	
Blood sampling for PK, PD, IG	Refer to Attachment 4 , Attachment 5 , and Attachment 6 .							
Efficacy Assessments								
Imaging studies (CT/MRI)						X	Radiographic assessment of tumor response should be performed prior to the start of a cycle so that results are available before the patient receives a new cycle of treatment.	
Bone scan	X*						Breast cancer cohort: Routine bone scans during treatment are not required, except in the setting of bone-only disease (no lymph node, visceral, skin, or subcutaneous metastases), or as deemed appropriate by the investigator. *Prostate cancer cohort: Follow-up (posttreatment) bone scans are required every 6 weeks, or as clinically indicated.	

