Tumor assessments						X	Radiographic assessment of tumor response should be performed prior to the start of a cycle so that results are available before the patient receives a new cycle of treatment.	

Procedure	Treatment Cycle 3 and beyond						Comments
	Day 1	Day 8	Day 15	Day 22	Day 29	Day 36	
Ad hoc tumor tissue and blood sampling			X				Optional: Additional tumor tissue and/or blood samples for biomarker research may be obtained at the investigator's discretion in discussion with the patient, such as at the time of radiographic response or treatment progression. If, at any time during the study, tumor tissue is obtained through a core biopsy, surgical biopsy, or resection as routine clinical care, the sponsor requests a tissue block or unstained slides for analysis of potentially relevant surrogate biomarkers.
Study Therapy Administration							
Administer LY3022855 Weekly (on Days 1, 8, 15, 22, 29, and 36)	X	X	X	X	X	X	For patients being treated on Dosage C and who are clinically benefitting, after the completion of Cycle 3, the dosing interval may be changed to once-every-2-week dosing after discussion with the sponsor. If a patient's dosage is changed from that of Dosage C (that is, weekly) to every-2-week dosing and then the patient develops progressive disease, the patient's dosage may then be changed back to weekly dosing if agreed upon by the investigator and sponsor.
Administer LY3022855 Every 2 Weeks (on Days 1, 15, and 29)	X		X		X		
Administer LY3022855 on Weeks 1, 2, 4, and 5 (on Days 1, 8, 22, and 29)	X	X		X	X		

Abbreviations:  $\beta$ -hCG = beta human chorionic gonadotropin; AE = adverse event; CA 15-3 = cancer antigen 15-3; CEA = carcinoembryonic antigen; CK = creatine kinase; CT = computed tomography; ECG = electrocardiogram; ECOG PS= Eastern Cooperative Oncology Group performance status; IG = immunogenicity; MRI = magnetic resonance imaging; PET = positron emission tomography; PD = pharmacodynamic(s); PK = pharmacokinetic(s); SAE = serious adverse event; ULN = upper limit of normal; WOCBP = women of childbearing potential.

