6.1. General Considerations

Statistical analysis of this study will be the responsibility of the sponsor. The analyses for this study will be descriptive, except for exploratory analyses of biomarker data, as deemed appropriate. Analyses of the biomarker data will be described in a separate biomarker SAP.

Data analyses will be provided by cancer type, dose group, and for all study patients combined, wherever appropriate. For continuous variables, summary statistics will include number of patients, mean, median, standard deviation, minimum, and maximum. Categorical endpoints will be summarized using number of patients, frequency, and percentages.

The following data handling conventions will be used in the analysis (see [Table 6.1](#)).

Table 6.1. Data Handling Conventions

Term	Definition or Rule
Relative Study Day	If assessment is on or after date of first dose then (date of assessment) – (date of first study drug dose) +1
	If assessment precedes first dose of drug then (date of assessment) – (date of first study drug dose)
	There is no study day 0. Study day 1 is the date of first dose and study day -1 is the day before the first dose.
Baseline	For change from baseline analyses, baseline value is defined as the last reported measure on or before the first dose date (prior to the dose administration), unless, otherwise, specified. For change from baseline within a cycle, baseline value is defined as the measure prior to the first dose of that cycle, unless, otherwise, specified.
Entered	Patients who have signed the informed consent document directly.
Enrolled population	Patients who have been assigned to study treatment and have received at least 1 dose of any study treatment.
Screen Failures	Patients who have signed informed consent, do not meet eligibility criteria and are not enrolled.
Evaluable population	Patients who complete 1 cycle of LY3022855 treatment, undergo 1 baseline and 1 posttreatment tumor biopsy procedure, and complete immune blood studies for 1 cycle
Safety Population	Patients who have received at least 1 dose of study drug.

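### From Cycle 2, adverse events are asked about only on dosing days, so scheduled assessment differs by dosage (C 6, B 4, A and D 3 per cycle), although every dosage has weekly blood tests in Cycle 2

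*Protocol*

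**What the plan says.** Protocol Section 8.1.2 ties routine AE assessment to the study schedule in Attachment 1. There, the Cycle 2 table, which covers all dosing schedules, carries the instruction "To be performed only on dosing days" in the toxicity/AE row and repeats it for concomitant medication, ECOG status and vital signs. The Cycle 3+ table uses the same wording. The dosing days are listed as "Weekly (on Days 1, 8, 15, 22, 29, and 36), Every 2 Weeks (on Days 1, 15, and 29"), plus Days 1, 8, 22 and 29 for the Weeks 1, 2, 4 and 5 schedule. Section 6.2 assigns breast cancer patients alternately to "Dosage C (LY3022855, 100 mg QW of a 6-week cycle) or D (LY3022855, 100 mg Q2W of a 6-week cycle").

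The same Cycle 2 table schedules hematology, serum chemistry and C-reactive protein on Days 1, 8, 15, 22, 29 and 36 for everyone: "Every week for the first 12 weeks on therapy". From Cycle 3, hematology and chemistry become "Every 2 weeks for patients receiving treatment on the Weekly or Every-2-Week dosing schedule".

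Cycle 1 uses one set of assessment days for all schedules. Its vital-signs comment adds that these are "also to be checked and recorded at nontreatment visits during Cycle 1". That comment concerns vital signs, not AEs, but it shows that off-dose visits were expected in Cycle 1.

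On analysis, SAP 6.1 states: "Data analyses will be provided by cancer type, dose group, and for all study patients combined, wherever appropriate". SAP 6.13 summarizes events by treatment group for the registry, including the number of events. SAP 6.9.2 defines and tabulates TEAEs by organ class, term and grade. None of the three mentions that assessment frequency differs by dosage.

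**The concern.** How often patients are asked about symptoms influences how many short or mild events are recorded. If one dosage is asked weekly and another fortnightly, a higher count under weekly dosing has two possible sources: the drug, or the more frequent asking. Dosages C and D share a 100 mg dose, are filled concurrently by alternating assignment, and have their safety data reviewed together with other data after about 3 cycles (protocol 10.9, SAP 6.11). A reader of the by-dosage tables will naturally set them side by side.

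In Cycle 2 the difference also seems avoidable, because blood tests are already scheduled on the off-dose weeks. In that cycle laboratory toxicity is sampled on the same days in all dosages, but symptoms are not.

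**Working it through.** There is no plan figure to reproduce; the check is a count of scheduled days.

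Inputs: dosing days and the dosing-days-only rule from the Attachment 1 Cycle 2 and Cycle 3+ tables; blood-test days from the same tables; schedule of each dosage from Table JSCB.1.

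**Step 1, Cycle 2.** Scheduled AE assessments equal the number of dosing days. Blood-test days without one are {1, 8, 15, 22, 29, 36} minus the dosing days. Intervals run to Day 1 of the next cycle (Day 43).

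| Dosage | Dosing days | AE assessments per cycle | Intervals (days) | Cycle 2 blood-test days without AE assessment |
|---|---|---|---|---|
| C | 1, 8, 15, 22, 29, 36 | 6 | 7 throughout | none |
| B | 1, 8, 22, 29 | 4 | 7, 14, 7, 14 | 15, 36 |
| A, D | 1, 15, 29 | 3 | 14 throughout | 8, 22, 36 |

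The C to D ratio is 6/3 = 2. CT/MRI and tumor assessment are also scheduled in Cycle 2 on Day 36, one of the days without an AE assessment for A, B and D.

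**Step 2, Cycle 3 onward.** Hematology and chemistry for both C and D fall on Days 1, 15 and 29. For D these are exactly the dosing days, so no off-dose blood-test visit remains at which an AE assessment could be added. The 6 versus 3 difference persists.

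**Step 3, up to the interim review at about 3 cycles.** Cycles 2 and 3 give C 2 × 6 = 12 and D 2 × 3 = 6. Assume Cycle 1 contributes the same number k to each dosage, with k = 6 if Day 36 counts and k = 5 if it does not (the Day 36 cell cannot be read with confidence in the available text).

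- As planned: C 12 + k, D 6 + k, that is 18 versus 12 (k = 6) or 17 versus 11 (k = 5).
- With Cycle 2 assessed weekly in D: D becomes k + 6 + 3, that is 18 versus 15 or 17 versus 14.

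The change therefore halves the gap over three cycles, from 6 assessments to 3, and removes it within Cycles 1-2.

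**Step 4, exposure.** Planned dose per cycle is 6 × 100 = 600 mg in C and 3 × 100 = 300 mg in D. Assessment frequency and planned exposure both differ by a factor of 2, so the planned tables cannot attribute an excess in C to one or the other.

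These are planned counts. Held doses lower them in any dosage. For a benefitting Dosage C patient, "after the completion of Cycle 3, the dosing interval may be changed to once-every-2-week dosing after discussion with the sponsor", which would bring that patient to 3 per cycle.

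**The case against.** The strongest reply is that little is left for the visit schedule to miss. Protocol 8.1.2.2.2 requires all on-therapy AEs to be reported whatever the visit day, so the next dosing-day assessment covers the interval. Patients are told to contact the investigator about problems with study drug (Section 7.2), and clinically significant laboratory findings must be reported as AEs. The CK and AST elevations emphasized in Section 5.4.5 rest on blood tests that are equally frequent in all dosages in Cycle 2 and, for chemistry, in C and D from Cycle 3. SAP 6.9.4 grades relevant laboratory values in addition to the reported AEs. All of this stands, and it confines the point to short, low-grade, non-laboratory events.

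The second reply concerns importance. A reader might infer that weekly versus 2-weekly tolerability is a main comparison of the study. The documents do not say so: the primary objective is immunomodulatory activity, safety is a secondary objective stated as a profile of the drug, the study is nonrandomized, and no safety contrast between C and D is specified. Nor does SAP 6.9.2 itself order TEAEs by dosage; that comes from the general statement in SAP 6.1, qualified there as applying where appropriate, and from SAP 6.13.

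Third, tying AE review to dosing days is a legitimate, openly stated choice. The amendment aimed to reduce physician visits, and Dosage D is justified partly by fewer clinic visits. Attendance on the off-dose days is inferred from scheduled procedures, and the blood tests may use a local or investigator-designated laboratory. This bears on cost. It does not remove the difference in scheduled assessment.

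**Conclusion.** The point holds as one of unequal scheduled ascertainment: from Cycle 2, planned AE and concomitant-medication assessments are 6 per cycle in C, 4 in B and 3 in A and D, and in Cycle 2 the difference arises on days that already carry scheduled blood tests. It could shift by-dosage counts of short, mild, non-laboratory TEAEs. Serious and Grade 3 or higher events should be little affected.

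The 2:1 ratio counts visits and does not measure bias. It is tempting to conclude that events are lost in D, or that part of any excess in C is due to the schedule. The documents support neither conclusion: they contain no figure on recall or ascertainment, reporting is required regardless of visit day, and C's doubled planned exposure could produce a genuine excess. The effect is of unknown size.

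The verdict assumes that patients attend on the scheduled blood-test days and that the Cycle 1 assessments apply alike to all dosages. It does not call the study into question; it supports an inexpensive improvement that makes the descriptive safety tables easier to interpret.

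**What to change.** **Attachment 1, Cycle 2.** Perform the toxicity/AE and concomitant-medication assessments on all six scheduled weekly days in every dosage. This adds Days 8, 22 and 36 for A and D, and Days 15 and 36 for B. Confirm that Cycle 1 Day 36 is treated alike in all dosages.

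**SAP 6.9.2.** Beside the overall TEAE table, add a by-dosage table restricted to Cycles 1-2, where scheduled assessment would then be equal. If the schedule is not changed, restrict that table to Cycle 1. In either case, add a note that scheduled assessments still differ from Cycle 3 (6 for C versus 3 for D) and that this cannot be separated from the difference in exposure.

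**Cost.** Some staff and investigator time on three off-dose days per A or D patient and two per B patient in Cycle 2, including the relatedness judgment for any event found; somewhat more arrangement where the blood is drawn at a local laboratory; and one extra table. No new visit day is added to the schedule.
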